5.3 Dose Limiting Toxicity (DLT)

Toxicity will be assessed according to the NCI Common Terminology Criteria for Adverse Events Version 4.0 (CTCAE v4.0).

The Dose Limiting Toxicity Period will be the first 14 days from the start of the CED procedure.

Dose limiting toxicity (DLT) will be defined as:

- Any intolerable (as deemed by the patient or investigator) grade 2 or any grade 3 or higher neurological toxicity felt to be attributable to the CED infusion procedure or to the MTX110 injection with gadoteridol within a period of 14 days after the infusion.
- Any systemic treatment related grade 3 or higher hematologic or non-hematologic toxicity (after maximal medical management of nausea/vomiting/diarrhea) within a period of 14 days after the infusion.

If multiple toxicities are seen, the presence of a dose limiting toxicity should be based on the most severe toxicity experienced.

Dose modifications are described in Section 5.5.

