7. ADVERSE EVENTS

An adverse event (also known as an adverse experience) within this protocol is defined as any untoward medical occurrence associated with the study procedure (placement of catheters) or use of the drug, whether or not considered to be procedure or drug related. (Please follow directions for routine reporting provided in the Data Reporting section). Additionally, all serious adverse events must be reported in an expedited manner to allow for optimal monitoring of subject safety and care. The Expedited Reporting sections in this protocol provide guidelines for expedited reporting.

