7.1 Adverse Event Characteristics

- **CTCAE term (AE description) and grade:** The descriptions and grading scales found in the revised NCI Common Terminology Criteria for Adverse Events (CTCAE) version 4.0 will be utilized for AE reporting. All appropriate treatment areas should have access to a copy of the CTCAE version 4.0. A copy of the CTCAE version 4.0 can be downloaded from the CTEP web site http://ctep.cancer.gov/protocolDevelopment/electronic_applications/ctc.htm.

Surgical adverse events that cannot be graded by CTCAE terminology (e.g., prolonged intubation) will be reviewed on a weekly basis by the Investigator and by the Data and Safety Monitoring Committee (DSMC) per their established reviewing schedule. Please see Appendix E PNOC Data Safety and Monitoring Plan for more information. All other events that can be graded by CTCAE terminology will use the CTCAE grading. This includes wound infections, hemorrhage, cerebral spinal fluid (CSF) leak, and respiratory and neurologic adverse events.

- **Attribution** of the AE:
 - Definite – The AE *is clearly related* to the study treatment including surgical procedure.
 - Probable – The AE *is likely related* to the study treatment including surgical procedure.
 - Possible – The AE *may be related* to the study treatment including surgical procedure.
 - Unlikely – The AE *is doubtfully related* to the study treatment including surgical procedure.
 - Unrelated – The AE *is clearly NOT related* to the study treatment including surgical procedure.

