9.1 Response Criteria

9.1.1 Definitions

Evaluable for toxicity. All subjects will be evaluable for toxicity from the time of their first treatment with MTX110 injection.

Evaluable for objective response. Only those subjects who have measurable disease present at baseline, have received at least one cycle of therapy, and have had their disease re-evaluated will be considered evaluable for response. These subjects will have their response classified according to the definitions stated below. (Note: Subjects who exhibit objective disease progression prior to the end of cycle 1 will also be considered evaluable.)

Evaluable Non-Target Disease Response. Subjects who have lesions present at baseline that are evaluable but do not meet the definitions of measurable disease, have received at least one cycle of therapy, and have had their disease re-evaluated will be considered evaluable for non-target disease. The response assessment is based on the presence, absence, or unequivocal progression of the lesions.

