10.5 Analysis of Endpoints

Intent-to-Treat Population (ITT): The ITT population will include all subjects who are enrolled in the study. The ITT population will be the primary population for evaluating efficacy and subject characteristics.

As-Treated Population (AT): The AT population will include all subjects who receive at least 1 dose of study drug. The AT population will be the primary population for evaluating safety.

Analysis of Primary Endpoint

- Safety of repeated CED of MTX110 following standard of care focal radiotherapy will be assessed by monitoring for adverse events, scheduled laboratory assessments, vital sign measurements, and physical examinations for subjects who receive the drug. The severity of toxicities will be graded according to the NCI CTCAE v4.0. Adverse events and clinically significant laboratory abnormalities (meeting Grade 3, 4, or 5 criteria according to CTCAE) will be summarized by maximum intensity and relationship to study drug(s). Grade 1 and 2 adverse events will be summarized if related to study therapy. Descriptive statistics will be utilized to display the data on toxicity.

Analysis of Secondary Endpoint

- We will assess the preliminary efficacy using overall survival at 12 months (OS12) in 19 evaluable DIPG patients treated within the expansion cohort which will include subjects treated as part of the dose escalation portion of the trial on the recommended phase 2 dose (RP2D). Analyses will be performed after all enrolled subjects have completed 12 months, or whenever the status of all subjects has been established, whichever comes first. The primary analysis will be based on the Kaplan-Meier method. Kaplan-Meier estimates and the associated 95% CIs will be calculated for OS12. As described above, if 12 or more of the 19 patients are alive at 12 months, the null hypothesis that OS12 is 40% will be rejected.

Analysis of Exploratory endpoint

The exploratory aims associated with this study will be descriptive and will be limited to frequency tables and summary statistics.

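### The primary safety population requires a dose of drug, so a child harmed at first catheter placement and never infused drops out of the primary safety summary

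*Combined protocol and SAP*

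**What the plan says.** Section 10.5 defines two populations. ITT is all enrolled subjects and is primary for efficacy and subject characteristics. AT is primary for safety: "The AT population will include all subjects who receive at least 1 dose of study drug". The analysis of the primary endpoint repeats the limit, listing adverse events, laboratory tests, vital signs and "physical examinations for subjects who receive the drug". Section 9.1.1 is in line with this: "All subjects will be evaluable for toxicity from the time of their first treatment with MTX110 injection".

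Other sections treat the CED procedure as part of what is being tested:

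- Section 7 defines an adverse event as "any untoward medical occurrence associated with the study procedure (placement of catheters) or use of the drug".
- Every attribution category in 7.1 refers "to the study treatment including surgical procedure".
- Section 5.3 counts as dose-limiting any qualifying neurological toxicity "felt to be attributable to the CED infusion procedure or to the MTX110 injection with gadoteridol", and states: "The Dose Limiting Toxicity Period will be the first 14 days from the start of the CED procedure".
- The stopping rules in 10.3 include one for more than 20% of subjects going uninfused because of surgical complications at placement.

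**The concern.** Under 5.1, anaesthesia, catheter placement and a confirming MRI all come before infusion. A serious complication at that stage can itself be the reason no drug is given. A population that requires a dose then removes the child because of the event that the safety analysis is meant to count. The bias has one direction for placement harm: the reported rate can only fall.

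The primary objective concerns MTX110 given by intratumoral CED, and the primary endpoint in 10.1 is the safety of repeated CED administration. A reader of the primary safety table would take it to describe the risk of the whole intervention. A serious first-placement injury in a child who was never infused would not appear in it.

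A smaller wording problem sits beside this one. Section 10.5 summarises grade 3 to 5 events by relationship to study drug but selects grade 1 and 2 events by relation to study therapy, while the only attribution scale, in 7.1, includes the surgical procedure.

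**Working it through.** **Reading the text.** The question is how an analysis population is defined, so the plan has no figure to reproduce.

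1. Who is in AT? Only subjects with at least one dose (10.5). The protocol does not define a dose. Section 5.2.3 has the catheter primed with the drug mixture before insertion, but nothing says that priming counts.
2. Can a subject undergo the procedure and receive no dose? Yes. Placement precedes infusion (5.1), and 10.3 has a stopping rule for this case.
3. Does any other section bring that subject into the primary safety summary? No. ITT is assigned to efficacy and subject characteristics, 9.1.1 starts toxicity evaluability at first treatment, and no population is defined by procedure started.
4. Are the data collected? Yes. Reporting runs from consent (7.3), surgical complications are documented (7.2.1), and the DSMC reviews serious events (7.2). The child is missing from the analysis set, not from the database.
5. Are later cycles affected? No. A child harmed at a later placement has already been dosed and is in AT.

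The DLT status of an uninfused child is also unclear. In 5.3 the DLT period opens at the start of the procedure, while both DLT criteria count 14 days after the infusion. Those statements need reconciling.

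**Size.** The documents give no rate of failed first placement, so the event counts below are assumptions. Inputs: N = 26, the minimum enrolment in 3.2, with all 26 starting placement; k children harmed (grade 3 or higher) at first placement and never infused; x infused children with a grade 3 or higher event. The AT proportion is x/(N − k). The proportion among procedures started is (x + k)/N. Intervals are exact (Clopper-Pearson) 95%.

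| x | k | AT set | Procedures started |
|---|---|---|---|
| 0 | 1 | 0/25 = 0% (0 to 13.7%) | 1/26 = 3.8% (0.1 to 19.6%) |
| 0 | 2 | 0/24 = 0% (0 to 14.2%) | 2/26 = 7.7% (0.9 to 25.1%) |
| 3 | 1 | 3/25 = 12.0% (2.5 to 31.2%) | 4/26 = 15.4% (4.4 to 34.9%) |
| 3 | 2 | 3/24 = 12.5% (2.7 to 32.4%) | 5/26 = 19.2% (6.6 to 39.4%) |

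**How large could k become?** Two rules in 10.3 limit it. One irreversible grade 3 or higher neurological deficit definitely related to the procedure already stops the study for review. The 20% rule does not say when it is checked.

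- If it is checked as subjects accrue (an assumption), a first non-infusion among the first four subjects exceeds it (1/4 = 25%), as does a second among the first nine (2/9 = 22.2%). The fractions 1/5 and 2/10 equal 20.0% and do not.
- If it is applied only to the final total, 5/26 = 19.2% would not exceed it.

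**The case against.** The best defence is that a dosed set suits a study of a drug: a child who never receives MTX110 says nothing about drug or infusion toxicity. The harm is also handled where it matters for the children in the trial. Serious events are reported within one business day regardless of relationship, the DSMC sees them, and stopping rules address both placement failure and procedural deficits. Calling AT primary does not forbid a further table. The affected group is narrow, the counts above are assumed, and the paired intervals overlap heavily. Widening the denominator also slightly dilutes drug-related rates: 3/25 = 12.0% becomes 3/26 = 11.5%.

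Much of this stands as a limit on weight. Safety monitoring is not deficient, and no test, sample size or dose decision changes. The attribution wording carries little weight, because the scale in 7.1 already covers the procedure.

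It does not remove the point. The endpoint is the safety of CED administration, of which placement is a part. No supplementary table is specified. DSMC review does not correct the primary summary. The dilution is half a percentage point, and a retained table of dosed subjects answers it.

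**Conclusion.** The concern holds. Followed as written, 10.5 excludes a child from the primary safety summary because of an outcome that the summary should count, and it understates placement harm. In the illustrations, one such child in 26 lowers the reported grade 3 or higher rate by 3.4 to 3.8 percentage points (15.4% − 12.0%; 3.8% − 0%). Two lower it by 6.7 to 7.7 points (19.2% − 12.5%; 7.7% − 0%). These sizes rest on assumed counts, on N = 26, and on every subject starting placement. If no child is harmed at first placement and left uninfused, the omission of harmed children has no effect. The consequence is limited to a descriptive table, so this should be corrected but does not threaten the conduct of the trial.

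**What to change.** Make three wording changes:

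1. In 10.5, define the primary safety population as every subject in whom a CED procedure is started (anaesthesia or catheter placement), whether or not MTX110 is infused, and drop the repeated restriction to subjects receiving drug.
2. In 9.1.1, start toxicity evaluability at the start of the first CED procedure.
3. In 10.5, summarise events by relationship to study treatment including the surgical procedure, to match 7.1.

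Keep the dosed subset as a supporting table, so that drug-related rates are also shown on the exposed denominator.

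The cost is small. The events are already collected from consent, and no sample size, test or escalation rule changes. The headline toxicity rate may look slightly less favourable. If procedure and drug attribution are to be reported separately, the case report form needs a small clarification. The change should be made before safety results are summarised, so that counting a harmed child is not decided after the fact.

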¹ from October 2016

Summary of adverse events with cut off date Oct 31, 2018 of the current study.

To date, we have enrolled █ subjects and completed monitoring and DSMC approval of the first 4 dose levels as per the ATD. There were no DLTs at any dose level. Table 13 details related adverse events reported to date.

Table 13. Adverse events probably, possibly or definitely related to protocol therapy:

			Maximum grade across all cycles			
			Grade 1	Grade 2	Grade 3	Grade 4
Toxicity	Dose level	# Evaluable Patients				
Fatigue	4	1	1	-	-	-

Summary of preclinical and clinical data

In summary, the relevant preclinical and clinical studies support the exploration of CED of MTX110 in children with DIPG:

- (1) The target of MTX110 is highly expressed in human DIPGs
- (2) Human derived DIPG cell lines are sensitive to MTX110
- (3) CED leads to effective distribution within the brainstem
- (4) CED of MTX110 under real time imaging is feasible
- (5) Published evidence supports the feasibility of CED in children with DIPG
- (6) Five total pediatric patients with DIPG receiving MTX110 via CED support safety of delivery of MTX110 via the proposed CED protocol.

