5.2 Dose Administration

Table 5.2.1. Dose levels.

Dose level	Concentration MTX110	Total Volume (ml)	Day of therapy
1	30 μ M	3	Day 1
2	30 μ M	6 (3mL each day)	Day 1, 2
3	30 μ M	8 (4mL each day)	Day 1, 2
4	30 μ M	10 (5mL each day)	Day 1, 2
5	30 μ M	12 (6mL each day)	Day 1, 2
6	60 μ M	12 (6mL each day)	Day 1, 2
7	90 μ M	12 (6mL each day)	Day 1, 2

If dose levels 6 or 7 are not tolerated, dose de-escalation levels will be implemented as per Table 5.2.2. For example, if dose level 6 is not tolerated, dose level 5a will be tested and if dose level 7 is not tolerated, dose level 6a will be tested.

Table 5.2.2. Optional dose de-escalations pending toxicity.

Dose level	Concentration MTX110	Total Volume (ml)	Day of therapy
5 ^a	45 μ M	12 (6mL each day)	Day 1, 2
6 ^a	75 μ M	12 (6mL each day)	Day 1, 2

- MTX110 will be delivered by 1 or 2 catheters surgically placed in an intratumoral (IT) location.
- The concentration of gadoteridol (ProHance®) will be 0.5 mM for both dose levels; both agents will be combined and co-infused using the same catheters.
- Maximum infusion rate will be increased as stated above in 5.1, utilizing the same criteria for escalation as will be used for overall dose level escalation (section 10.2).
- Timing of 2nd infusion (applicable to dose level 2 and higher) will be determined pending subject's return to pre-infusion baseline neurological exam or \leq grade 1 toxicities (with exception of toxicities anticipated to be within normal limits of post-operative recovery-listed below), but will occur no later than 48 hours after completion of infusion on day 1, i.e. if subject's neurological exam has not returned to pre-infusion baseline or has evidence of toxicities $>$ grade 1 by 48 hours from completion of day 1 infusion, the 2nd CED procedure will be canceled.
- The following toxicities are anticipated to be within normal limits of post-operative recovery and will not preclude initiation of the 2nd (day 2) infusion:

- Grade 2 headache
 - Grade 2 pain
 - Grade 2 nausea
- If vomiting occurs during post-operative recovery, initiation of the 2nd (day 2) infusion may proceed only if vomiting is improving and the participant has 4-6 hours without emesis prior to dose administration.

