7.2.1 Surgical Adverse Event Grading

Anticipated Adverse Effects

Complications related to the surgical procedure will be documented. ‘Minor’ are those defined as leading to little or no effect on function, and not resulting in a significant increase in hospital stay. ‘Major’ complications are those resulting in permanent sequelae with functional limitations, or those leading to a significant increase in hospital stay. Surgical adverse events that cannot be graded by CTCAE terminology (e.g., prolonged intubation) will be reviewed on a weekly basis by the Investigator and by the Data and Safety Monitoring Committee (DSMC) per their established reviewing schedule. All other events that can be graded by CTCAE terminology will use the CTCAE grading. This includes wound infections, hemorrhage, cerebral spinal fluid (CSF) leak, and respiratory and neurologic adverse events.

7.3 **Adverse Event Reporting**

All Adverse Events (AEs) will be entered into OnCore®. Appendix D includes detailed information about PNOC reporting timelines.

The study period during which AEs and SAEs must be reported begins after informed consent is obtained and ends 30 days following the last administration of study treatment. After this period, only SAEs that are attributable to study treatment should be reported. Subjects removed from therapy for unacceptable adverse event(s) will be followed until adverse event(s) resolves or returns to baseline status.

The PNOC Investigator will assign attribution of the possible association of the event with use of the study therapy, and this information will be entered into OnCore®. The Investigator must also comply with all reporting requirements to their institutional Data and Safety Monitoring Committee (DSMC) and Institutional Review Board (IRB).

7.4 **Serious Adverse Events and Expedited Reporting**

All Adverse Events which meet the definition of ‘Serious’ as well as other medically significant events described below require expedited reporting to PNOC. Below are instructions for recording and reporting of these events. Please contact the PNOC Operations Office [REDACTED] with any questions regarding expedited reporting requirements for this study. See 7.1.3 for the definition of an SAE.

All SAEs (see above definition) on any PNOC trial, regardless of relationship, must be reported to PNOC via OnCore and Email within one business day of first PI awareness, even if the SAE is ongoing. The SAE must be followed until resolution:

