10. STATISTICAL CONSIDERATIONS

10.1 Study Design/Endpoints

This is an open-label, prospective, multi institutional safety and early efficacy protocol. All subjects will be treated at a PNOG Institution or participating institution for this study. The primary endpoint is safety; the secondary endpoint is a preliminary estimate of efficacy.

Primary Endpoint:

- Safety and toxicity measurements of repeated CED administration of MTX110 following standard of care focal radiotherapy using CTCAE version 4.0 in newly diagnosed subjects with DIPG.

Secondary Endpoint:

- OS at 12 months (OS12) in newly diagnosed subjects with DIPG.

[figure not shown]
Exploratory Endpoints:

- Assessment of observed distribution of gadoteridol compared to pre-treatment modeling of the drug distribution utilizing predictive imaging software.
- The Quality of Life exploratory endpoint associated with this study will be descriptive and will be limited to frequency tables and summary statistics.
- To perform central review of imaging to explore MR qualitative and quantitative measures as markers of disease response and/or progression and treatment effect in comparison to institutional evaluation of disease response and/or progression.

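### Section 10.5 summarises grade 1–2 adverse events only if rated related, and gives surgical complications that CTCAE cannot grade no place in the primary safety result

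*Combined protocol and SAP*

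**What the plan says.** Section 10.1 defines the primary endpoint as "Safety and toxicity measurements of repeated CED administration of MTX110 following standard of care focal radiotherapy using CTCAE version 4.0".

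Collection is broad. Section 7 counts an untoward event "whether or not considered to be procedure or drug related", and Section 7.3 adds: "All Adverse Events (AEs) will be entered into OnCore". Section 7.1 gives five levels of attribution, from definite to unrelated, and words each in terms of the study treatment with the surgical procedure included.

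The analysis in Section 10.5 is narrower. Grade 3, 4 and 5 events are summarised by worst intensity and by relationship to the study drug. For the lower grades the rule is: "Grade 1 and 2 adverse events will be summarized if related to study therapy". A closing sentence says in general terms that toxicity data will be shown with descriptive statistics.

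Section 7.2.1 has surgical complications documented and divides them into minor and major. For those outside CTCAE it says: "Surgical adverse events that cannot be graded by CTCAE terminology (e.g., prolonged intubation) will be reviewed on a weekly basis by the Investigator", with DSMC review on that committee's own schedule. Section 10.5 mentions neither the minor/major classes nor ungradable events.

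**The concern.** The primary objective is safety and tolerability of repeated intratumoral infusion. New neurological signs in these children may come from the tumour, the catheter procedure or the drug, and there is no control arm to separate them. Attribution is weakest in this setting, yet it decides whether a grade 1–2 event appears in the primary result. Two investigators with the same events and different habits of attribution would produce different safety profiles.

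Grade 2 events also have a formal role in the design, since they can end the accelerated phase. A reader of the final report should be able to find every event that could have driven that step. The burden of repeated catheter placement, at intervals of 4–8 weeks, is part of tolerability as well, including complications that have no CTCAE term.

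**Working it through.** The plan gives no figure on this point to reproduce. The check sets what is collected beside what 10.5 summarises.

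| Type of event | Collected | Summarised under 10.5 |
|---|---|---|
| Grade 3–5, any attribution | Yes (7, 7.3) | Yes; relationship to drug named, procedure not named |
| Grade 1–2, rated related | Yes (7, 7.3) | Yes |
| Grade 1–2, not rated related | Yes (7, 7.3) | No |
| Surgical, gradable by CTCAE (wound infection, hemorrhage, CSF leak, respiratory, neurologic) | Yes (7.1, 7.2.1) | Yes, under the rows above |
| Surgical, not gradable by CTCAE | Yes, as minor or major (7.2.1) | No summary named |

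1. *Where the line falls.* Section 10.5 does not define 'related'. If it follows the grouping in the title of Table 13 (definite, probable, possible), the grade 1–2 events lost are those rated unlikely or unrelated.

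2. *Link to escalation.* Sections 5.5 and 10.2 move the trial to a 3+3 design at the second occurrence of any grade 2 toxicity in the first cycle, with no attribution condition stated. A grade 2 event rated unlikely can therefore be one of the two that trigger the change and still fall in the third row of the table.

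3. *DLTs.* Section 5.3 makes an intolerable grade 2 neurological event a DLT only if it is attributed to the infusion procedure or the injection. Such an event is already rated related, so 10.5 keeps it, provided that 'study therapy' includes the procedure.

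4. *Drug or procedure.* Section 7.1 attributes events to drug and procedure together. Section 10.5 uses study drug in one sentence and study therapy in the next, and defines neither.

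5. *Ungradable events.* The endpoint is defined by CTCAE and the summary is by CTCAE grade. An event with no grade has no row in such a table.

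6. *Size.* The documents give no rate for unrelated grade 1–2 events or for ungradable surgical events, so the number omitted cannot be calculated. As an illustration for the surgical part only, assume that a proportion p of subjects has at least one ungradable event. The chance of seeing one or more such subjects among n is 1 − (1 − p)^n. With n = 19 (the efficacy cohort) and n = 26 (the minimum enrolment in 3.2):

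| Assumed p | n = 19 | n = 26 |
|---|---|---|
| 2% | 32% | 41% |
| 5% | 62% | 74% |
| 10% | 86% | 94% |
| 20% | 99% | 99.7% |

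The values of p are assumptions. The table shows only that the case need not be remote; it does not estimate what would be omitted.

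**The case against.** The best defence is that little is lost and nothing depends on it. The attribution scale includes the procedure, and Table 13 counts possible as related, so post-operative events attributed to surgery would stay in. Most serious surgical events have CTCAE terms; the only ungradable example given is prolonged intubation. All adverse events are reviewed weekly by the operations office (7.2), the DSMC sees ungradable surgical events (7.1, 7.2.1), and the supplier receives a tabulation of all events every three months (7.4.5). Escalation follows the DLT and grade 2 rules, not the 10.5 summary. All of this stands, and it confines the point to the reported endpoint.

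Two textual defences do not stand. The grade 3–5 parenthesis in 10.5 could be read as applying to laboratory values only, but the next sentence would then be redundant for adverse events. The general sentence on descriptive statistics does not undo an explicit restriction.

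A reader might also infer more than the documents support:

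- *That grade 2 DLTs disappear from the summary.* They do not, because Section 5.3 requires attribution.
- *That Table 13 shows the restriction at work.* Its title reads "Adverse events probably, possibly or definitely related to protocol therapy", and it shows a single grade 1 fatigue, while Section 5.2 says of grade 2 headache, pain and nausea: "The following toxicities are anticipated to be within normal limits of post-operative recovery and will not preclude initiation of the 2nd (day 2) infusion". But Table 13 limits every grade to related events, which 10.5 does not do. Section 5.2 gives no rate, and accelerated cohorts are single subjects. The table is background and says nothing about how much 10.5 would omit.
- *That ungradable surgical events are excluded by rule.* Section 10.5 is silent on them; the gap is an omission.

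**Conclusion.** The point holds as a defect in the primary safety summary. Section 10.5 makes the low-grade profile depend on a subjective rating, can leave out a grade 2 event that counted toward the design transition, does not say whether relationship covers the procedure, and names no summary for surgical complications without a CTCAE grade. It is worth correcting because safety is the primary endpoint and the data are already held.

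It is not a failure of collection or of DSMC oversight, and it does not alter the escalation rules. Its size is unknown. The conclusion assumes that 10.5 would be applied as written and that 'related' would be read as possible, probable or definite; a stricter reading would drop more events.

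**What to change.** In Section 10.5, replace the sentence on grade 1–2 events with text to this effect:

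- All adverse events of every grade are summarised by worst grade, regardless of attribution.
- A second table gives the same events by attribution. 'Related' means possible, probable or definite, and covers both the drug and the surgical procedure. The same term is used for every grade.
- A further table gives minor and major surgical complications as classed in 7.2.1, including those that CTCAE cannot grade, per procedure. It should state whether placements that ended without infusion are counted: the As-Treated population requires at least one dose, while a stopping rule in 10.3 counts subjects who were not infused.

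The cost is wording in one section and two or three longer descriptive tables. No new data are needed, because all events, the attribution rating and the minor/major class are already to be recorded.

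Two extensions are not proposed. A shift table of neurological findings from the pre-infusion examination would need a scoring scale, and Sections 6.1 and 6.2 specify none. Separate drug and procedure columns would need separate ratings, which 7.1 does not describe.
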